Specific Aim #2: Evaluate the effects of the above treatments on CAVC progression (secondary endpoint) measured using multi-detector computed tomography (MDCT) at baseline, 6 months and after one and two years of treatment.

Other Secondary Endpoints: Bone serum biochemical parameters obtained at quarterly monitoring visits: FGF23, sclerostin, DKK1, PTH, the PTH 1-84/PTH N-terminal truncated fragment ratio, TRAP-5b, BSAP, and P1NP.

Analyses will also be performed to identify links between the response of these serum biochemical parameters to the treatments and changes in bone mass and CAVC. These data should provide novel information on potential mechanisms for both bone loss and CAVC progression.

This study is a logical continuation of our NIH funded studies that have established the severity of bone loss in CKD-5D patients and its association with vascular calcifications. These severe clinical problems have major morbidity and mortality and are routinely

untreated. The results of this study will provide proof of concept for a greatly needed low bone densityosteoporosis treatment regimen by differentiating turnover status and race in CKD-5D patients.

Study Design: Describe the study design (e.g., single/double blind, parallel, crossover, etc.). Indicate whether or not the subjects will receive placebo medication at some point in the research procedures. Also, indicate whether or not the subjects will be randomized in this study. You may reference sponsor's protocol pages and attach as an appendix in the E-IRB "Additional Information" section, however, a summary paragraph must be provided in the text box below. (Including the study design table from a sponsor's protocol is helpful to IRB members.)

Community-Based Participatory Research: If you are conducting [community-based participatory research \(CBPR\)](#), describe strategies for involvement of community members in the design and implementation of the study, and dissemination of results from the study.

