Research Repositories: If the purpose of this submission is to establish a Research Repository (bank, registry) indicate whether the material you plan to collect would or would not be available from a commercial supplier, clinical lab, or established IRB approved research repository. Provide scientific justification for establishment of an additional repository collecting duplicate material. Describe the repository design and operating procedures. For relevant information to include, see the UK Research Biospecimen Bank Guidance [\[PDF\]](#) or the UK Research Registry Guidance [\[PDF\]](#)

Patient recruitment will be done for the first 42 months of the study after administrative startup (Figure 2). Biochemical measurements, MDCT, QCT and DXA scans, and clinical assessment will be performed at baseline, 6 months, and at 12 months, 18 months and 24 months. Treatment monitoring visits with blood draws (initially bi-weekly or monthly and thereafter every 3 months) and adverse event monitoring phone calls (monthly at least) will occur during years one through five. Interim analyses and first publications will be done once 50% of patients have completed 1 year visits, approximately at the end of Year 3. Final analyses of the data and preparation of abstracts and manuscripts of the obtained results will be completed during year 5. Control patients who completed 1 year of follow up without treatment will be offered additional 2 years of enrollment with treatment according to protocol. Patients who were initially randomized to treatment groups will be offered continued treatment for an additional 1 year to complete 2 years of therapy. Previously enrolled patients will be recruited from the beginning of patient enrollment. These patients will be provided with an additional consent for the extension of the treatment arm.

Figure 2: Study Timeline

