Patients consenting for baseline measurements will have BMD measurements of the total hip, lumbar spine and radius by DXA and total body scan. We do not use QCT for initial BMD assessment to avoid unnecessary radiation exposure to patients with normal bone mass who will be excluded from the study. Patients who are not do not have low bone densityosteoporotic by DXA T-scores/Z-

scores at any site will be excluded from further participation. Results from our prior funding period study indicate this will be 30% or 178 patients. Those patients who are identified as having low bone density/osteoporotic will have blood draws performed for determination of turnover status (PTH, PTH ratio and TRAP-5b; see Table 1) and baseline biochemical results (serum calcium and BSAP). They will also have BMD measurements of the total hip and spine by QCT, and CAVC measured by MDCT. Patients will be assigned to one of two treatment arms based on their turnover status: 1) low turnover patients and 2) normal or high turnover patients. For each treatment arm we will use adaptive randomization by group completion rates, age race and gender to assign patients to one of two groups A) treatment, and B) no study treatment (standard of care) controls.

For the extension of treatment modification, we will contact all patients who completed one year in either the treatment or control arms. Patients who previously participated in the treatment arm will be offered an additional 1 year of therapy to complete 2 years of therapy. For patients who previously participated in the control arm, they will be offered 2 years of therapy. Both therapies can be given in two consecutive years, or with a time-gap in-between.

TREATMENT PROTOCOLS:

Low Turnover Groups: Patients with low bone turnover will be randomized to receive daily teriparatide injections with cinacalcet or no study treatment, i.e. standard of care, as controls.

Normal or High Turnover Groups: Patients with normal or high bone turnover will be randomized to receive alendronate or no study treatment, i.e., standard of care, as controls. Teriparatide is not justified in these patients because it might worsen underlying high turnover abnormalities and requires avoidable daily injections.

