Table 2. Detail of Blood Draws for Monitoring Safety and Compliance and Secondary Endpoint Serum Biochemical Parameters
Teriparatide

Treatment Group Base-line Bi-weekly visits until steady state Q1 Visit Q2 Visit Q3 Visit 1 Year 15 mo 18mo 21mo 2 yr
or Safety: Serum Calcium & PTH X X X X X X X X X X X X

For Compliance: BSAP X X X X X X X X X X

Secondary Endpoints: FGF23, P1NP, Sclerostin, DKK-1 & PTH Ratio X X X X X

Alendronate

Treatment Group Base-line Monthly visits until steady state Q1 Visit Q2 Visit Q3 Visit 1 Year 15 mo 18mo 21mo 2yr

For Safety and Compliance: BSAP X X X X X X X X X X

Secondary Endpoints: Serum Calcium, PTH & PTH Ratio, FGF23, P1NP, Sclerostin, DKK-1 X X X X X

Standard of Care Controls Base-line Q2 Visit 1 Year 15mo 18mo 21mo 2 yr

Secondary Endpoints: All of the above Serum Biochemical Parameters X X X X X

Cinacalcet will be adjusted in 30 mg steps up to a maximum daily dose of 180 mg if needed to keep intact PTH at levels less than 200 pg/mL. If by six weeks, this fails to achieve PTH levels less than 200 pg/mL, patients will be excluded from further study participation. In the rare case where PTH level maintenance requires cinacalcet doses that induce serum calcium levels below 8.5 mg/dL, treatment will cease for two weeks after which calcium will be re-measured. At two weeks if calcium remains below 8.5 mg/dL, patients will be excluded from further participation in the study. If calcium is normalized, cinacalcet will be reinstated at half of the prior dose. Calcium will be checked again at the next monitoring visit. If at any measurement point PTH levels are less than 60 pg/mL cinacalcet will be withheld and reinstated if levels are again above 200 pg/mL.

Treatment Protocol for Alendronate: Patients with normal or high bone turnover will receive a starting dose of 35 mg alendronate p.o. once per week. Patients will be carefully instructed to follow the manufacturer's recommendations for administration. Serum calcium will be rechecked 1 week +/- 3 days after starting therapy. Dosage will be adjusted according to changes in the bone turnover marker

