BSAP from blood drawn at monthly monitoring visits for the first 3 months, thereafter at quarterly monitoring visits. BSAP is expected to go down, but to avoid over-suppression, will not be allowed to go below the low normal range of the assay, as is done clinically. Our data show that mid/normal ranges of these markers in CKD-5D patients indicate low turnover^{48, 49} If this safety threshold is crossed, treatment will be stopped until values are back above the threshold at a regularly scheduled monitoring visit. Once demonstrably back within safety threshold, treatment will be reinstated at half of the initial dose (35 mgs every other week). If BSAP does not go down at least 8% over a one month period, treatment doses will be doubled to 70 mgs per week. If they still remain high, study coordinators will carefully review with the patients the mode of drug intake and possible compliance lapses.

Primary Endpoint At one year after baseline, we will assess bone mass using QCT BMD measurements of the total hip and compare 1 and 2 year changes in bone mass between the treatment and control groups. Total hip will be used as the primary endpoint site because in our prior funding period we showed that changes at the total hip in QCT BMD are more pronounced than at the spine⁶. The Secondary endpoint will be differences between the treatment and control groups in changes in coronary artery calcifications by MDCT. This will be relevant regardless of bone effects.

Other secondary endpoints tracked at baseline, 6 months, and 1 year, 18 and 24 months will include serum biochemical markers of bone activity; FGF 23, BSAP, TRAP5b, P1NP, Sclerostin, and DKK1.

Additionally we will record 1) Change in QCT BMD of the spine to compare with the hip) 2) Changes in DXA BMD of the hip and spine (to determine whether the more commonly available DXA results are equivalent to QCT and 3) Changes in aortic and heart valve calcification (to compare with the coronary artery calcifications).^{50,51} 4) Whole body composition (%fat vs %lean) as it relates to survival in CKD-5D patients.

Attachments

Attach Type	File Name
ResearchProcedures	figure 3 7.22.2019 pdf.pdf

Data Collection: List the data or attach a list of the data to be collected about or from each subject (e.g. interview script, survey tool, data collection form for existing data).

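### The blood-draw schedule (Table 2) leaves out TRAP-5b, a named secondary endpoint, and the sections disagree on whether the markers are quarterly or six-monthly

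*Combined protocol and SAP*

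**What the plan says.** Objectives (Other Secondary Endpoints) gives a frequency and opens the list: "Bone serum biochemical parameters obtained at quarterly monitoring visits: FGF23, sclerostin, DKK1, PTH". Four more markers follow there: a PTH ratio, TRAP-5b, BSAP and P1NP.

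Study Design gives a different frequency: "Biochemical measurements, MDCT, QCT and DXA scans, and clinical assessment will be performed at baseline, 6 months, and at 12 months, 18 months and 24" (the last figure is also in months). It describes the three-monthly treatment monitoring visits separately.

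Research Procedures, in the paragraph on endpoints, agrees with Study Design: "Other secondary endpoints tracked at baseline, 6 months, and 1 year, 18 and 24 months will include serum biochemical markers of bone activity". The markers it then names are "FGF 23, BSAP, TRAP5b, P1NP, Sclerostin, and DKK1".

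Earlier in Research Procedures, patients with low bone density have "blood draws performed for determination of turnover status (PTH, PTH ratio and TRAP-5b; see Table 1"), so TRAP-5b is planned at baseline before randomisation. Study Design specifies a TRAP-5b assay and its precision.

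Table 2, whose title covers safety, compliance and secondary-endpoint draws, gives the teriparatide group's marker row as "Secondary Endpoints: FGF23, P1NP, Sclerostin, DKK-1 & PTH Ratio". The alendronate row has the same five plus serum calcium and PTH. BSAP sits in a separate compliance row for each treated group. The control section has the columns "Standard of Care Controls Base-line Q2 Visit 1 Year 15mo 18mo 21mo 2 yr" and a single row that points back to the parameters above it.

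**The concern.** A schedule-of-assessments table is what coordinators tend to work from at a visit. If it omits an endpoint that the text requires, the sample may not be assayed, and the loss may not be noticed until analysis.

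TRAP-5b matters more than its place as one of eight suggests. Background promises markers of both bone resorption and bone formation, and Specific Aim 1 gives alendronate to reduce resorption. Background calls BSAP a formation marker and pairs P1NP with it. FGF23, the Wnt-pathway indicators (sclerostin, DKK1) and the PTH measures are other kinds of marker. By elimination TRAP-5b is the resorption marker, although the documents never label it so. Without follow-up values, the alendronate comparison has no direct resorption readout after baseline, and the planned analyses linking marker response to bone mass and calcification lose that marker.

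The timing conflict raises a second question: at which visits can treated patients be compared with controls at all?

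**Working it through.** No sample size, power or alpha figure is involved. The check sets the marker lists and visit columns side by side.

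**Marker lists**

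| Marker | Objectives | Table 2 (any row) | Research Procedures, endpoint paragraph |
|---|---|---|---|
| FGF23 | yes | yes | yes |
| Sclerostin | yes | yes | yes |
| DKK1 | yes | yes | yes |
| P1NP | yes | yes | yes |
| BSAP | yes | yes | yes |
| TRAP-5b | yes | **no** | yes |
| PTH | yes | yes | no |
| PTH ratio | yes | yes | no |

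TRAP-5b is the only marker in Objectives that Table 2 lacks (1 of 8). The control row cannot restore it, because it only refers to what stands above. In the other direction, the endpoint paragraph omits PTH and the PTH ratio, though its wording leaves the list open.

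**Frequency over 0 to 24 months**

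- Quarterly (Objectives): 24/3 + 1 = 9 time points.
- Six-monthly (Study Design, Research Procedures): 24/6 + 1 = 5 time points.
- Table 2: the secondary-endpoint row of each treated group carries 5 marks against 10 columns. Five marks fit the six-monthly schedule. The positions of the marks were lost in text extraction (one row shows 12 marks for 10 columns, and the control row 5 for 7), so this is an inference from the count and the other two sections. Row labels and column headings are readable.

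**Visits with and without controls**

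- Treated columns: baseline, early visits to steady state, Q1, Q2, Q3, 1 year, 15, 18 and 21 months, 2 years.
- Control columns: baseline, Q2, 1 year, 15, 18 and 21 months, 2 years.
- Treated columns with no control column: the early visits, Q1 (month 3) and Q3 (month 9). Of the four quarterly points in year 1, controls have two (6 and 12 months).
- Rows that reach Q1 and Q3: BSAP in both treated groups (10 marks, 10 columns) and, in effect, calcium and PTH in the teriparatide group. Among the endpoint markers, the draws without control values at months 3 and 9 are therefore BSAP in both treated groups and PTH with teriparatide.
- FGF23, P1NP, sclerostin, DKK1 and the PTH ratio appear to have no month-3 or month-9 draw in any group. They would lack controls at those visits only if the quarterly statement in Objectives governed.

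**After one year.** Study Design and Research Procedures offer active treatment to controls who complete one year. The control columns from 15 months on therefore need not describe untreated patients.

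**The case against.** The strongest reply is that this is a slip in a table. A reader of Table 2 might infer that TRAP-5b is not collected. The documents do not support that: it is drawn at baseline for turnover status, has a specified assay, and is listed at 6, 12, 18 and 24 months in Research Procedures. This stands. The loss is conditional on staff following Table 2 rather than the text.

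A reader might also infer that all month-3 and month-9 marker values lack controls. Under Table 2 that is true only of BSAP and teriparatide-group PTH. Those rows are labelled for safety or compliance, which untreated controls do not need, and no section plans a quarterly between-group marker analysis. This stands too.

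Nor is TRAP-5b the only turnover marker apart from the formation markers: Background and Research Procedures use PTH and the PTH ratio to determine turnover. The supportable statement is that it is the only apparent resorption marker.

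Finally, two sections agree on six-monthly timing, which leaves Objectives as the outlier, and the point touches neither the primary endpoint (hip BMD by QCT) nor coronary calcification. That limits the importance of the point but does not remove the contradiction. Table 2 presents itself as the schedule for these endpoints and omits one of them.

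**Conclusion.** The point holds as an internal inconsistency worth correcting. Table 2 omits TRAP-5b for both treated groups and, by reference, for controls, while Objectives and Research Procedures make it a secondary endpoint. If Table 2 is followed alone, 4 of the 5 planned TRAP-5b time points (6, 12, 18 and 24 months) are at risk in every group.

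The stated frequency differs, nine time points against five. Under Table 2, BSAP in both treated groups and PTH in the teriparatide group are drawn at months 3 and 9 without control values.

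Confidence is high on the TRAP-5b omission, the conflict between the text sections and the missing control columns, since these rest on readable labels and sentences. It is lower on which visits the marks in Table 2 denote. That TRAP-5b is the resorption marker is inferred by elimination.

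**What to change.** 1. Add TRAP-5b to the secondary-endpoint rows of Table 2 for the teriparatide and alendronate groups, and name it explicitly for controls, using draws already scheduled.
2. Make Objectives, Study Design, Table 2 and the endpoint paragraph of Research Procedures agree on one marker list, including whether PTH and the PTH ratio belong to it, and on baseline, 6, 12, 18 and 24 months. In Objectives, replace the quarterly statement.
3. State that randomised between-group marker comparisons use only visits at which both groups are sampled and controls are still untreated, chiefly 6 and 12 months. Describe treated-only BSAP and PTH values at other visits as monitoring data, and later values as extension data.

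The cost is wording plus one additional assay per scheduled visit: four per patient after baseline (5 − 1) for a patient followed to 24 months. No new visit is needed. The documents do not describe stored serum, so values for visits already completed may not be recoverable. If some were missed, the analysis should report how many and treat them as missing.

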Serum Biochemical Parameters. Blood draws and laboratory analysis will be performed by the Center for Clinical and Translational Science (CCTS). Blood specimens may also be obtained in tubes by the dialysis staff, for pick up by the coordinators, at the time the patient is receiving dialysis to minimize additional patient venipuncture. Serum calcium will be measured using routine laboratory technique (Roche autoanalyzer). Plasma intact and 1-84 PTH levels will be measured by a radioimmunoassay (Scantibodies, Santee, CA). The intra- and interassay coefficients of variation for intact PTH are <5 and <7%, and for 1-84 PTH <6 and <8%. BSAP levels will be measured using an EIA (Metra BAP EIA, Quidel, San Diego, CA). The intra- and inter-assay coefficients of variation are <6% and <8%. TRAP-5b levels will be determined using an EIA (MicroVue, Quidel, Santa Clara, CA). The intra- and inter-assay coefficients of variation are <2.2% and <3%. P1NP levels will be measured using an ELISA (USCNK, Wuhan, China); the intra- and inter-assay coefficients of variation are <9% and <10%. Serum sclerostin levels will be measured using an EIA (Tecomedical group, Sissach, Switzerland). The intra- and inter-assay coefficients of variation are <3.1% and <3.5%. Serum FGF23 levels will be measured by an ELISA (EMD Millipore, Billerica, MA). The intra- and inter-assay coefficients of variation are <8% and <12%. DKK1 will be determined by an ELISA (Biomedica, Vienna, Austria). The intra- and inter-assay coefficients of variation are <8% and <12%. Bone mineral density (BMD) Two techniques—DXA and QCT—will measure BMD. DXA measurements will be performed in the CCTS core facility. QCT measurements will be conducted in the UK Department of Radiology and qualitatively analyzed on a Syngo MMWP workstation and quantified in the Image Analysis Lab of the Division of Nephrology, Bone and Mineral Metabolism. Measurements will be performed using FDA approved imaging equipment, calibration phantoms, and post imaging analysis software/clients used in everyday clinical practice. (The medical center is on a regular schedule of equipment upgrades and, consequently, the specific equipment utilized will change periodically.) Imaging equipment will be maintained and calibrated using manufacturer recommended techniques and schedules. The studies will be performed under the supervision of, and interpreted by, board certified physicians.

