Coronary, Aortic and Valve Calcification (CAVC): CAVC will be assessed using MDCT. Non-contrast computed tomography will be performed on a 64 Slice Dual Source CT Somatom Definition scanner (Siemens AG, Erlangen, Germany). Images will be acquired from 3cm above the aortic arch to 2 cm below the heart. Scan parameter are the following: non-ECG gated 64 x 0.6 collimation, 120 kVp, quality reference mass 160mAs, 0.33 sec gantry rotation time (QUICK) and 3 mm slice thickness. Images will be analyzed on a 3D workstation using calcium scoring software (HeartView CT, Siemens AG, Erlangen, Germany). Calcifications are identified as a plaque of =1 mm² with a density of =130 HU and quantified using the previously described Agatston scoring method.⁵³ Intra and inter-observer error for interpretation of images is <1% based on our prior funded studies. Intra-observer error was determined through comparison of repeated interpretation 2-4 weeks apart. In addition same scan inter-observer variability was determined (through repeat measurements 30 minutes apart) to be <1% based on our prior funded studies.

CAVC will also be determined at baseline, 6 months and at one year intervals using the square root of volume (CAVC SRV) an analytic method that accounts for interscan variability,^{54, 55} and CAVC density. We will calculate the area of the plaque by dividing the CAVC volume by the thickness of the slice (3 mm). Density will then be calculated by taking the Agatston score divided by the area.³⁹ Some patients will have coronary artery and vascular stents, coronary artery bypass changes, intraluminal catheters and automated implantable cardioverter-defibrillators. In patients with coronary artery stents, the CAVC scores will be obtained both with and without inclusion of the stents. Artifacts from metal or catheters including streak will be excluded by hand while drawing regions of interest. Attempts will be made to scan patients with acceptable heart rates, less than 80-100 bpm, to reduce motion artifact. In the case of coronary artery motion artifact, regions of interest will be drawn to exclude motion oriented inflation of CAVC scores. In severe cases of motion patients will be rescanned. Single rescans are deemed acceptable radiation exposure. Similar daily, weekly and yearly calibration scans will be obtained according to the manufacturer's recommended procedure as discussed in the QCT paragraph above.

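### Treatment is compared with no treatment and no masking of the CT readers is stated, which leaves the coronary calcification endpoint, and to a lesser degree hip QCT, open to reader bias

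*Combined protocol and SAP*

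**What the plan says.** Under Research Procedures, each turnover arm is randomized to treatment or "no study treatment (standard of care) controls". In the low-turnover arm, "Patients with low bone turnover will be randomized to receive daily teriparatide injections with cinacalcet or no study treatment". In the other arm, "Patients with normal or high bone turnover will be randomized to receive alendronate or no study treatment". No placebo is described.

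The Study Design prompt asks the investigator to "Describe the study design (e.g., single/double blind, parallel, crossover, etc". The study text below it does not say whether patients, staff or image readers are blinded.

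For the primary endpoint, "we will assess bone mass using QCT BMD measurements of the total hip" at one year, and one- and two-year changes are compared between groups. The bone mineral density paragraph says the QCT scans are "quantified in the Image Analysis Lab of the Division of Nephrology, Bone and Mineral Metabolism". It describes calibration phantoms and analysis software, and a measurement precision of 0.8% is given.

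The secondary endpoint is the between-group difference in change in coronary artery calcification by MDCT. The calcification paragraph sets area and density thresholds and uses Agatston scoring in software. It then adds manual steps: "Artifacts from metal or catheters including streak will be excluded by hand while drawing regions of interest", and where there is coronary motion "regions of interest will be drawn to exclude motion oriented inflation of CAVC scores". Severe motion leads to a rescan. Patients with coronary stents are scored both with and without the stents. Intra- and inter-observer error is put below 1%, from earlier studies. Radiology co-investigators supervise the analysis and alert the PI promptly to clinically important observations.

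Coding of patient identity appears under Safety Precautions and again under Confidentiality, in both places as a privacy measure.

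**The concern.** With drug against no treatment, allocation is not hidden by the design, so an objective endpoint is protected only if those who quantify the images do not know the group. If a reader knows or can guess the group, choices about which pixels are artifact or motion can differ slightly between groups without any intent. The same applies to visit order: a reader who knows which scan is the follow-up may expect progression or its absence. Visit can also hint at treatment, because controls may be offered study drug after one year.

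A difference of this kind enters the estimated treatment effect directly. It does not shrink with sample size, and for a fixed tilt a larger trial is more likely to declare it significant. The Background section states that the team expects calcification progression to fall under treatment, so the likely direction of any tilt is towards benefit.

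**Working it through.** **Part 1: what the text supports for each endpoint.**

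| | Hip QCT (primary) | Coronary calcification (secondary) |
|---|---|---|
| Comparator | No study treatment | No study treatment |
| Masking to group stated | No | No |
| Masking to visit order stated | No | No |
| Manual exclusion or hand-drawn regions described | No | Yes, for metal, catheter and motion artifact |
| Who quantifies or supervises | Laboratory of a nephrology and bone division | Radiology co-investigators supervise |
| Quality figure given | Precision 0.8% | Observer error below 1% |

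The two quality figures describe repeatability, and phantom checks test the scanner. None of these would show a systematic difference in reading between groups. The two lists of people with access to the identity codes do not include image readers, but neither section says that readers are kept from allocation or visit order.

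**Part 2: how much a tilt could matter.** The plan gives no figure to reproduce: the supplied text states no group size for the comparison, no SD of change, no alpha and no power. Every input below is therefore an assumption, on a BMD-type percentage-change scale:

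- 100 patients per group
- SD of change 4% or 6%
- two-sided 5% test
- average between-group reading tilt of 0.2%, 0.5% or 1%

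Formulas: SE = SD × √(2/100). Type I error = P(|Z + tilt/SE| > 1.96), with Z standard normal.

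- SD 4: SE = 4 × 0.1414 = 0.566
- SD 6: SE = 6 × 0.1414 = 0.849

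| Average tilt | tilt/SE (SD 4) | Type I error (SD 4) | tilt/SE (SD 6) | Type I error (SD 6) |
|---|---|---|---|---|
| 0.2% | 0.35 | 6.4% | 0.24 | 5.6% |
| 0.5% | 0.88 | 14% | 0.59 | 9% |
| 1% | 1.77 | 42% | 1.18 | 22% |

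With 50 per group (SE 0.80 or 1.20), a 1% tilt gives 24% or 13%.

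The tilt is an average over all patients. If only those with artifact are affected, it is diluted: a 1% tilt in 20% of patients (assumed) averages 0.20 × 1% = 0.2%, the first row. In 50% of patients it averages 0.5%, the second row. These percentages should not be read across to Agatston or volume scores, whose spread the documents do not give.

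**The case against.** The strongest reply is that much of the measurement is constrained. Calcification uses fixed thresholds and software scoring, severe motion is rescanned, and stents are scored both ways. The discretionary exclusions concern metal, catheters and motion, and only some patients have such devices. This stands as a limit on size, and it is why the smaller tilts belong in the table. It does not remove the discretion. The scans are not ECG-gated, so some coronary motion is foreseeable, and the supplied text does not say which of the two stent scores counts.

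A second reply is that silence is not evidence of unmasked reading. This also stands: the study design graph and the procedures figure are not shown, and the text does not say that readers know the group. The supportable statement is that masking is not stated.

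Some stronger readings are tempting but unsupported:

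- A reader might infer that hip BMD is also measured with hand-drawn regions. Both passages on regions of interest belong to the calcification paragraph; the QCT text describes no manual exclusion.
- A reader might infer that QCT is quantified in the trial's own division. The text gives the laboratory's division and the PI's specialty, but does not state the PI's division.
- A reader might take the observer error of below 1% as evidence of a 1% bias. It is a repeatability figure and says nothing about a difference between groups.

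A practical objection to masked reading is delay. Holding all of a patient's scans until the last one would conflict with the interim analysis planned once half the patients have their one-year visit, and with the semiannual analyses under Data and Safety Monitoring. That objection is sound, and the fix has to avoid it.

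**Conclusion.** The point holds, with different weight for the two endpoints. As written, the plan leaves coronary calcification open to reader bias: there is no placebo, no reader masking is stated, and discretionary manual exclusions are described. Hip QCT shares the missing masking but not the documented hand work, so its exposure is smaller.

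The size cannot be derived from the documents. Under the assumptions shown, the type I error ranges from about 6% at an average tilt of 0.2% to between 22% and 42% at 1%. The 42% is the top of an assumed range and should not be quoted as an estimate of what will happen. The conclusion rests on the design and the absence of stated masking, and needs none of these figures.

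It should be acted on because the safeguard is cheap and no later analysis can separate a reading tilt from a treatment effect. If readers are already masked to group and visit, a sentence saying so settles most of the point, leaving only the written exclusion rules.

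**What to change.** State in the imaging paragraphs of Study Design that:

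- the existing readers quantify all QCT and MDCT scans from files carrying a study code that hides treatment group and visit order;
- written rules, fixed before masked reading begins, govern the exclusion of artifacts, motion and stents from the calcification score, and name which stent score is used for the endpoint;
- each reading, including its regions of interest, is locked before it is linked to group;
- scans are read in batches timed to each planned analysis, and are not held until a patient's last scan;
- the prompt look for clinically important findings stays separate from the masked quantification, so that alerts to the PI are not delayed.

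If images from completed visits are archived, they can be re-read under the same rules. The cost is relabelling of files, a short set of reading rules and slightly later readings. No extra readers are needed.
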